10.5.3.4. Day 1 (Baseline/Randomization and Lurasidone or Placebo Injection Dosing)

The following study related procedures will be performed predose:

- Awaken Subject.
- Provide Meals.
- Obtain Vital Signs.
- Perform 12-Lead ECG.
- Collect Blood and Urine Samples for Clinical Laboratory Tests (time-matched to Predose on Day -7):
 - Hematology
 - Serum Chemistry
 - Urinalysis
 - Lipid Panel
 - Thyroid Panel
 - Coagulation Panel
- Collect Blood Sample for Serum Prolactin.
- Collect Blood Sample for PK (predose).
- Collect Urine Sample for PK (-0.5 to 0 hours predose).
- Administer PANSS.
- Randomize Subject.
- Dispense Lurasidone or Placebo Injection.
- Administer Lurasidone or Placebo Injection.
- Record Concomitant Medications.
- Record Adverse Events.

The following study related procedures will be performed postdose:

• Subject Injection Site Pain Assessment immediately postdose, and 6 hours and 12 hours postdose. A window of +1 minute is allowed for the immediately after

injection timepoint, and a window of \pm 5 minutes is allowed for the 6 and 12 hour timepoints.

- Investigator Injection Site Safety Assessment immediately postdose, and 6 hours and 12 hours postdose. A window of +1 minute is allowed for the immediately after injection timepoint, and a window of ± 5 minutes is allowed for the 6 and 12 hour timepoints. In addition subjects will be monitored for potential allergic reaction for 15 minutes after injection. A window of 0-5 minutes is allowed for this assessment.
- Obtain Vital Signs at 6 and 12 hours postdose.
- Perform 12-lead ECG at 6 and 12 hours postdose.
- Collect Blood Sample for PK at 2, 4, 6, 12 hours postdose.
- Collect Urine Sample for PK at 0 to 24 hours postdose.
- Administer C-SSRS (Since Last Visit version) at 12 hours postdose.
- Record Concomitant Medications.
- Record Adverse Events.

10.5.3.5. Days 2 to 8 (Safety and Tolerability Observation)

The following study related procedures will be performed:

- Awaken Subject (daily).
- Provide Meals (daily).
- Subject Injection Site Pain Assessment on Days 2 and 8.
- Investigator Injection Site Safety Assessment (daily).
- Obtain Vital Signs on Days 3, 5, and 7(time-matched to the injection predose timepoint on Day 1).
- Perform 12-Lead ECG on Days 3, 5, and 7 (time-matched to the injection predose timepoint on Day 1).
- Collect Blood and Urine Samples for Clinical Laboratory Tests on Day 8 (time-matched to the injection predose timepoint on Day 1):
 - Hematology
 - Serum Chemistry
 - Urinalysis
- Obtain Blood Sample for Serum Prolactin (Day 8).
- Collect Blood Sample for PK at 24, 48, 72, 96, 120 and 144 hours post-injection dose.
- Collect Urine Sample for PK at 24 to 48, 48 to 72, 72 to 96, 96 to 120, and 120 to 144 hours post-injection dose.
- Administer C-SSRS on Day 7.

- Administer PANSS on Day 8.
- Record Concomitant Medications (daily).
- Record Adverse Events (daily).

10.5.3.6. Days 9 to 14 (Safety and Tolerability Observation)

The following study related procedures will be performed:

- Awaken Subject (daily).
- Provide Meals (daily).
- Investigator Injection Site Assessment (daily).
- Obtain Vital Signs on Days 9, 11, and 13 (time-matched to the injection predose timepoint on Day 1)
- Perform 12-Lead ECG on Days 9, 11, and 13 (time-matched to the injection predose timepoint on Day 1).
- Record Concomitant Medications (daily).
- Record Adverse Events (daily).

10.5.3.7. Day 15 (Safety and Tolerability Observation)

- Awaken Subject.
- Provide Meals.
- Subject Injection Site Pain Assessment.
- Investigator Injection Site Safety Assessment.
- Perform Physical Examination.
- Obtain Vital Signs (time-matched to the injection predose timepoint on Day 1).
- Perform 12-Lead ECG (time-matched to the injection predose timepoint on Day 1.
- Collect Blood and Urine Samples for Clinical Laboratory Tests:
 - Hematology
 - Serum Chemistry
 - Urinalysis
 - Lipid Panel
 - Thyroid Panel
 - Coagulation Panel
- Collect Blood Sample for Serum Prolactin.
- Blood Sampling for Serum PK.

- Administer C-SSRS (Since Last Visit version).
- Administer PANSS.
- Record Concomitant Medications.
- Record Adverse Events.
- Schedule Next Visit.
- Discharge Subject (if subject is clinically stable in the Investigator's opinion).

10.5.3.8. Day 22 (Safety and Tolerability Observation)

Subjects may remain inpatient at the Investigator's discretion throughout the Treatment and Observation Period.

Subjects who have been discharged on Day 15 will have a clinic visit on Day 22.

The following study related procedures will be performed:

- Awaken Subject (daily if inpatient).
- Provide Meals (daily if inpatient).
- Obtain Vital Signs on Day 22 (approximately time-matched to the injection predose timepoint on Day 1).
- Perform 12-Lead ECG on Day 22 (approximately time-matched to the injection predose timepoint on Day 1).
- Collect Blood and Urine Samples for Clinical Laboratory Tests on Day 22 (time-matched to the injection predose timepoint on Day 1):
 - Hematology
 - Serum Chemistry
 - Urinalysis
- Obtain Blood Sample for Serum Prolactin on Day 22.
- Obtain Blood Sample for PK On Day 22.
- Administer C-SSRS on Day 22.
- Administer PANSS on Day 22.
- Schedule Next Visit.
- Discharge Subject (if clinically stable in the Investigator's opinion).
- Subject Injection Site Pain Assessment on Day 22.
- Investigator Injection Site Safety Assessment on Day 22.
- Record Concomitant Medications.
- Record Adverse Events.

10.5.4. Days 29 to 33 (End of Safety and Tolerability Observation and Beginning of Restabilization)

Subjects are required to be inpatient Days 29 to 33. Day 29 is the end of the safety and tolerability observation period for lurasidone injectable suspension/placebo injection. Day 29 is also the start of the restabilization period.

Restabilization' refers to the reintroduction of each subject's prior medications that were taken prior to entry into the study including their psychotropic medications. For early termination patients who received lurasidone dosing, following follow-up procedures they will need to be restabilized following the restabilization procedures.

Subjects who discontinue the study prior to Day 29 will undergo assessments scheduled for Day 29 at the time of discontinuation.

10.5.4.1. Day 29 (End of Safety and Tolerability Observation and Beginning of Restabilization)

- Awaken subject (if inpatient).
- Provide meals (if inpatient).
- Admit subject to clinic (if previously discharged).
- Perform Physical Examination.
- Record Weight and BMI.
- Obtain Vital Signs (approximately time matched to the injection predose timepoint on Day 1).
- Perform 12-Lead ECG (approximately time matched to the injection predose timepoint on Day 1).
- Collect Blood and Urine Samples for Clinical Laboratory Tests on (time matched to the injection predose timepoint on Day 1):
 - Hematology
 - Serum Chemistry
 - Urinalysis
 - Lipid Panel
 - Coagulation Panel
 - Thyroid Panel
- Obtain Blood Sample for Serum Prolactin.
- Obtain Blood Sample for PK.
- Obtain Blood Sample for b-hCG Serum Pregnancy Test (female subjects).
- Obtain Urine Sample for Urine Drug Screen and Urine Alcohol Test.
- Administer C-SSRS (Since Last Visit version).

- Administer PANSS.
- Subject Injection Site Pain Assessment.
- Investigator Injection Site Safety Assessment.
- Record Concomitant Medications.
- Reintroduce prior psychotropic medications.
- Record Adverse Events.

10.5.4.2. Days **30-32** (Restabilization)

The following procedures will be performed:

- Awaken Subject.
- Provide Meals.
- Continue prior psychotropic medications.
- Record Concomitant Medications.
- Record Adverse Events.

10.5.4.3. Day 33 (End of Restabilization)

The following study-related procedures will be performed:

- Awaken Subject.
- Provide Meals.
- Perform Physical Examination.
- Record Weight and BMI.
- Obtain Vital Signs (approximately time-matched to the injection predose timepoint on Day 1).
- Perform 12-Lead ECG (approximately time-matched to the injection predose timepoint on Day 1).
- Collect Blood and Urine Samples for Clinical Laboratory Tests (time-matched to the injection predose timepoint on Day 1):
 - Hematology
 - Serum Chemistry
 - Urinalysis
- Collect Blood Sample for Serum Prolactin.
- Administer C-SSRS (Since Last Visit version).
- Continue prior psychotropic medications.
- Record Concomitant Medications.

- Record Adverse Events.
- Schedule Next Visit.
- Discharge Subject.

10.5.5. Follow-up/Study Completion, Day 61 ± 2

All subjects will have an outpatient follow-up safety visit.

Subjects who discontinue the study after Day 29 but prior to Day 61 will undergo assessments scheduled for Day 61 at the time of discontinuation.

The following study-related procedures will be performed:

- Perform Physical Examination.
- Record Weight and BMI.
- Obtain Vital Signs.
- Perform 12-Lead ECG.
- Collect Blood and Urine Samples for Clinical Laboratory Tests:
 - Hematology
 - Serum Chemistry
 - Urinalysis
- Collect Blood Sample for Serum Prolactin.
- Collect Blood Sample for PK.
- Administer C-SSRS (Since Last Visit version).
- Record Concomitant Medications.
- Record Adverse Events.

11. SAFETY REPORTING

11.1. Definitions

11.1.1. Adverse Events

An AE is any untoward medical occurrence associated with the use of a drug in humans, whether or not considered drug related.

Untoward medical occurrences that occur between the time of signing the informed consent form (ICF) and drug administration are pre-treatment events. Those that occur after administration of study drug are considered AEs. Pre-treatment hospitalizations that occur in accordance with local clinical practice during the screening period (for wash-out from prior or concomitant medications) will not be considered as SAEs and do not need to be reported as such. Any untoward event that may occur during the hospitalization must be recorded as a pretreatment event. If hospitalization is prolonged by an untoward event, the event must be reported as an SAE.

An AE can, therefore, be any unfavorable and unintended sign (including an abnormal or clinically significant laboratory finding), symptom, or disease occurring after the administration of a medicinal (investigational) product, whether or not considered related to the medicinal (investigational) product. AEs may include the onset of new illness and the exacerbation of pre-existing conditions.

The Investigator should attempt to establish a diagnosis of the event based on signs, symptoms, and/or other clinical information. In such cases, the diagnosis should be documented as the AE and not the individual signs/symptoms.

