- n Investigator injection site safety assessment will include a rating of 1-4 on each of 4 items (pain, tenderness, erythema/redness, and induration/swelling). Assessments will be made on Day 1 (immediately after injection, and 6 hours and 12 hours after injection), Day 2 (24 hours after injection), Days 3-15 (daily during the inpatient period), Day 22, and Day 29. A window of +1 minute is allowed for the immediately after injection timepoint, and a window of ± 5 minutes is allowed for the 6 and 12 hour timepoints on Day 1. In addition subjects will be monitored for potential allergic reaction for 15 minutes after injection. A window of 0-5 minutes is allowed for the evaluation of potential allergic reaction.
- ^o Subjects will assess their injection site pain using a rating of 0-10 on a Likert Scale (0 = no pain, 10 = worst pain). This assessment will be completed prior to the Investigator injection site assessment on Day 1 (immediately after injection, and 6 hours and 12 hours after injection), Day 2 (24 hours after injection), Day 8, Day 15, Day 22, and Day 29. A window of +1 minute is allowed for the immediately after injection timepoint, and a window of ± 5 minutes is allowed for the 6 and 12 hour timepoints on Day 1.
- P Alternate subjects not included in the study cohort will be discharged following reintroduction of their prior medication if they are clinically stable (in the Investigator's opinion), subjects who received study drug will be eligible for discharge on Day 15 (but may remain inpatient at the Investigator's discretion up to Day 33), and early withdrawal subjects will be discharged after follow-up assessment procedures.
- ^q Concomitant medications will be recorded prior to and after oral and injection dosing.
- ^r In addition to any untoward medical occurrences in the subject (pre and postdose on dosing days), assessment of the injection site and monitoring of prodromal symptoms for seizures will be performed. If prodromal symptoms for seizure are found, additional neurological assessments will be done, as needed.

TABLE OF CONTENTS

RESTR	ICTED DISTRIBUTION OF PROTOCOLS	2
EMERO	GENCY CONTACTS	3
1.	SYNOPSIS	4
2.	LIST OF ABBREVIATIONS AND DEFINITIONS OF TERMS	22
3.	INTRODUCTION	25
3.1.	Background	25
3.2.	Study Conduct Rationale	26
3.3.	Risk-Benefit Assessment	26
4.	STUDY OBJECTIVES	26
4.1.	Safety Objective	26
4.2.	Pharmacokinetic and Pharmacodynamic Objectives	26
5.	STUDY ENDPOINTS	27
5.1.	Safety Endpoints	27

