• Injection site reactions will be assessed for severity according to each of the following categories (per the Investigator's judgement):

Local Reaction to Injectable Product	Mild (Grade 1)	Moderate (Grade 2)	Severe (Grade 3)	Potentially Life Threatening (Grade 4)
Pain	Does not interfere with activity	Repeated use of non-narcotic pain reliever > 24 hours or interferes with activity	Any use of narcotic pain reliever or prevents daily activity	Emergency room (ER) visit or hospitalization
Tenderness	Mild discomfort to touch	Discomfort with movement	Significant discomfort at rest	ER visit or hospitalization
Erythema/Redness	2.5 – 5 cm	5.1 – 10 cm	> 10 cm	Necrosis or exfoliative dermatitis
Induration/Swelling	2.5 – 5 cm and does not interfere with activity	5.1 – 10 cm or interferes with activity	> 10 cm or prevents daily activity	Necrosis

Reference: FDA Guidance for Industry "Toxicity Grading Scale for Healthy Adult and Adolescent Volunteers Enrolled in Preventive Vaccine Clinical Trials," 2007.

Adverse events, including SAEs, which start prior to study drug injection, will not be considered for stopping criteria.

Once a safety stopping criterion is reached, the study will not escalate beyond that dose level. If none of the stopping criterion has been attained, the study will proceed to the next higher dose level. Dosing of an additional cohort or cohorts at a dose between the identified MID and the highest dose below the MID may be conducted. The highest tolerated dose below the MID will be defined as the MTD for a single lurasidone injectable suspension dose.

If the MTD is not established, additional dose cohorts may be commenced until the MTD is reached.

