10.2.1. Pretreatment Events and Adverse Events

Pretreatment events will be recorded from the time informed consent is provided at screening until the time of first lurasidone oral tablet dose administration at Day -7.

Adverse events will be collected for each subject from immediately after the first lurasidone oral tablet dose administration at Day -7 until the follow-up visit at Day 61 (\pm 2).

Subjects should be queried in a non-leading manner, without specific prompting (eg, "Has there been any change in your health status since your last visit?"). See Section 11, Safety Reporting.

AEs and SAEs will be monitored throughout the study at all visits.

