11.3. Collection and Recording of Adverse Events

All pre-treatment events and AEs must be recorded in the subject's study records/source documents in accordance with the Investigator's normal clinical practice.

All pre-treatment events and AEs must be recorded on the CRF.

Pre-treatment events will be recorded from the time informed consent is provided at Screening until just prior to first lurasidone oral tablet study drug dose at Day -7. AEs will be recorded beginning after first study drug dose administration on Day 1 until the follow-up/study completion visit at Day 61 (\pm 2).

All AEs will be followed until resolution, stabilization of the condition, the event is otherwise explained, or the subject is lost to follow-up.

Each AE is to be evaluated for duration, severity, frequency, seriousness, action taken with the study treatment, outcome, and causal relationship to the study treatment. Definitions for severity, frequency, action taken with the study treatment, outcome, and causal relationship to the study treatment are presented below.

The severity of AE:

- **Mild** Ordinarily transient symptoms that do not influence performance of subject's daily activities. Other treatment is not ordinarily indicated.
- **Moderate** Marked symptoms sufficient to make the subject uncomfortable. Moderate influence on performance of subject's daily activities. Other treatment may be necessary.
- Severe Symptoms cause considerable discomfort. Substantial influence on subject's daily activities. May be unable to continue the study, and other treatment may be necessary.

The frequency of AE:

- Once an isolated episode.
- **Intermittent** occurs on two or more separate occasions.
- **Continuous** does not abate from date of onset to date of resolution.

The outcome of the AE:

- Recovered/Resolved
- Recovering/Resolving
- Not Recovered/Not Resolved
- Recovered/Resolved with Sequelae
- Fatal
- Unknown

The causal relationship of the AE to the study treatment:

Not related

o **Not related** – Improbable temporal relationship and is plausibly related to other drugs or underlying disease.

Related

- o **Possible** occurred in a reasonable time after study drug administration, but could be related to concurrent drugs or underlying disease.
- Probable occurred in a reasonable time after study drug administration, is unlikely to be attributable to concurrent drugs or underlying disease, and there is a plausible mechanism to implicate the study drug.

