## **7.2. BASELINE**

Unless otherwise specified, baseline is defined as the last non-missing measurement taken prior to  
Document:

Author:

Version Number:  
Version Date:

Final Draft  
11APR2019

Template No: CS\_TP\_BS016 Revision 4  
Effective Date: 01Apr2016

Reference: CS\_WI\_BS005

reference start date (including unscheduled assessments). In the case where the last non-missing measurement and the reference start date coincide, that measurement will be considered pre-baseline, but Adverse Events (AEs) and medications commencing on the reference start date will be considered post-baseline.

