#### **18.1. PRETREATMENT EVENTS AND ADVERSE EVENTS**

Pretreatment events will be recorded from the time informed consent is provided at screening until the Document:

Author:

Version Number:  
Version Date:

Final Draft  
11APR2019

Template No: CS\_TP\_BS016 Revision 4  
Effective Date: 01Apr2016

Reference: CS\_WI\_BS005

time of first lurasidone oral tablet dose administration at Day-7.

Adverse events will be collected for each subject from immediately after the first lurasidone oral tablet dose administration at Day -7 until the follow-up visit at Day 61 ( $\pm 2$ ). Adverse Events (AEs) will be coded using Medical Dictionary for Regulatory Activities (MedDRA) central coding dictionary, Version 21.0 or higher.

- Adverse Events for the Oral Lurasidone tablet period is defined as an AE that started on or after the first dose of the oral lurasidone tablet.
- Adverse Events for the double-blind Injection period is defined as an AE that started on or after the date of the double-blind injection.
- Adverse Events that started on the Oral Lurasidone tablet period and continued the double-blind injection, but the severity did not change the AE will be reported in the Oral Lurasidone tablet period. If the severity of the AE gets worse, the AE will be considered in the double-blind injection period.

AEs will be summarized by treatment and by MedDRA system organ class (SOC) and Preferred Term (PT).

An overall summary of number of subjects within each of the categories described in the sub-section below, will be provided as specified in the SAP.

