## DOUBLE-BLIND INJECTION PERIOD

START DATE	STOP DATE	ACTION
Known	Known	If start date < injection start date and after oral tablet, then not AE If start date >= injection start date, then AE
	Partial	If start date < injection start date and after oral tablet, then not AE If start date >= injection start date and after oral tablet, then AE
	Missing	If start date < injection start date and after oral tablet, then not AE If start date >= injection start date and after oral tablet, then AE
Partial, could be on or after injection start date	Known	If stop date >= injection start date, then AE
	Partial	Impute stop date as latest possible date (i.e. last day of month if day unknown or 31st December if day and month are unknown), then: If stop date >= injection start date, then AE
	Missing	Assumed AE

Document:

Author:

Version Number:  
 Version Date:

Final Draft  
 11APR2019

Template No: CS\_TP\_BS016 Revision 4  
 Effective Date: 01Apr2016

Reference: CS\_WI\_BS005

START DATE	STOP DATE	ACTION
Missing	Known	If stop date $\geq$ injection start date, then AE
	Partial	Impute stop date as latest possible date (i.e. last day of month if day unknown or 31st December if day and month are unknown), then: If stop date $<$ injection start date, then not AE If stop date $\geq$ injection start date, then AE
	Missing	Assumed AE

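### The SAP assigns AEs to study periods by calendar date, so an AE that starts on Day 1 before the injection is tabulated under the injected dose or placebo

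*Protocol*

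**What the plan says.** **SAP rules for the injection period.** All of them work on dates.
- SAP 18.1: "Adverse Events for the double-blind Injection period is defined as an AE that started on or after the date of the double-blind injection".
- SAP 7.2: "Adverse Events (AEs) and medications commencing on the reference start date will be considered post-baseline". The same section treats a measurement taken on that date as pre-baseline.
- SAP Appendix 2, double-blind injection period, known start date: "If start date >= injection start date, then AE". No line of the algorithm compares times.

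**SAP rule for the oral period.** SAP 18.1 counts from the first tablet dose, and repeats that events up to the time of that dose are pretreatment events. Appendix 2 turns this into a comparison of the start date with the tablet start date.

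**Carry-over.** SAP 18.1 keeps an AE that began in the oral period in that period if it continues at unchanged severity. It moves to the injection period only if it worsens.

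**Where the documents divide a dosing day at the dose.**
- Protocol 11.1.1, which separates pretreatment events from AEs: "Those that occur after administration of study drug are considered AEs".
- Protocol 9.3: "Adverse events, including SAEs, which start prior to study drug injection, will not be considered for stopping criteria".
- Protocol 10.2.1: "Adverse events will be collected for each subject from immediately after the first lurasidone oral tablet dose administration at Day -7". Anything earlier is a pretreatment event.
- Protocol Table 2 footnote r asks for untoward occurrences before and after dosing on dosing days, and 10.5.3.4 lists AE recording in both the predose and postdose blocks of Day 1.
- SAP 18.3 puts Day 1 predose ECGs in the oral period and starts the injection period with the Day 1 postdose timepoints.

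**Protocol text that does not line up.** Section 11.3 says "AEs will be recorded beginning after first study drug dose administration on Day 1", against Day -7 in 10.2.1. Section 10.5.3.1 lists AE recording before the Day -7 tablet, and Table 2 has no pretreatment-event entry for that day. Section 14.3.5.1 counts events on or after the study medication, without saying which medication or whether date or time decides.

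**The concern.** AE incidence by dose, severity and relationship is the main safety output of this first-in-human study of the injection. Under the date rule, an event that began overnight or during the predose procedures of Day 1 enters the column of a treatment the subject had not received.

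Day 1 predose is also a point at which findings tend to surface. Safety laboratory tests are taken on Day -8 and next on Day 1 predose, and ECGs on Day -6 and next on Day 1 predose. The two oral doses fall on Days -7 and -6. Protocol 11.2 records clinically significant laboratory and ECG abnormalities as AEs. A change caused by the tablets may therefore first be seen at the Day 1 predose visit. If it is dated to that visit, it leaves the oral column and enters a dose column. A Day 1 predose ECG abnormality would be an oral-period finding in the ECG table and an injection-period event in the AE table. The time-to-first-AE and incidence-by-study-day outputs in SAP 18.1.5 would also count such onsets on Day 1.

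**Working it through.** The plan states no figure on this point, so there is none to reproduce. The check applies the rules to test cases and then sizes the effect.

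**Step 1. Date rule against a dosing-time rule.** The left-hand result follows Appendix 2 and SAP 18.1. The right-hand result compares onset with the time of dosing.

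| Onset (known start, severity unchanged) | SAP date rule | Dosing-time rule |
|---|---|---|
| Day -7, before the tablet | oral | pretreatment |
| Day -5 | oral | oral |
| Day -1, 23:00 | oral | oral |
| Day 1, before injection | injection | oral |
| Day 1, after injection | injection | injection |

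Only the first and fourth cases change. The Day -7 case affects the oral column alone.

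**Step 2. Effect of one misassigned subject.** Each cohort doses 6 active and 2 placebo (protocol 14.1), with up to 5 cohorts and placebo pooled. That gives 5 × 6 = 30 active, 5 × 2 = 10 placebo and 40 in all.
- Dose group: 1/6 = 16.7 percentage points.
- Pooled placebo: 1/10 = 10.0 points.
- All active: 1/30 = 3.3 points.

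These are upper bounds. Protocol 14.3.5.1 counts a subject once per system organ class and preferred term, so a row moves only if the subject has no later event in it.

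**Step 3. How often.** The documents give neither an AE rate nor an injection time. Assume a 09:00 injection, so that 9/24 = 0.375 of Day 1 precedes it, and a constant onset rate r per subject-day.
- P(at least one in 6 subjects) = 1 − exp(−6 × 0.375 × r)
- Expected number in 40 subjects = 40 × 0.375 × r
- P(no AE in the 60 days after injection) = exp(−60 × r)

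| r (assumed) | At least one in a group of 6 | Expected in 40 | No later AE of any kind |
|---|---|---|---|
| 0.02 | 4.4% | 0.3 | 30% |
| 0.05 | 10.6% | 0.75 | 5% |
| 0.10 | 20.1% | 1.5 | 0.2% |

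An injection at 08:00 or 10:00 changes the predose share to 33% or 42%.

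A constant rate may be too low if findings cluster at the predose visit. Assume instead a probability p per subject of a Day 1 predose onset, with 1 − (1 − p)^n for at least one in n. For p = 1%, 2%, 5% and 10%, the chance is 6%, 11%, 27% and 47% in a group of 6, and 33%, 55%, 87% and 98% among 40.

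The last column of the table shows that the any-AE row would usually not move, because most affected subjects would have a later AE anyway. Individual preferred-term rows are where a shift could show.

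**The case against.** **The date rule is explicit and conservative.** It errs towards charging events to the injection and cannot hide a true post-injection AE. That stands as a reason to keep it when timing is unknown. It is not a reason to apply it when the event is known to precede the injection. The time of dosing is recorded (protocol 9.4).

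**The SAP does not plainly depart from the protocol's analysis text.** Section 14.3.5.1 also says on or after the study medication. This is fair. However, that wording neither calls for a date-only rule nor deals with two dosing periods, so it does not remove the conflict with 9.3 or with SAP 18.3.

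**Stronger readings that the documents do not support.**
- A reader might infer that every event present before the injection is charged to it. SAP 18.1 and Appendix 2 keep known earlier onsets in the oral period unless they worsen.
- A reader might infer that 11.1.1 alone contradicts the SAP. It does not. The first study drug is the Day -7 tablet, so under 10.2.1 a Day 1 pre-injection event is already an AE. The fault is the period to which it is attributed.
- A reader might infer that dose decisions are affected. Section 9.3 excludes these events, escalation rests on the Safety Review Team's judgement, and the SAP tables follow database lock. The two event sets differ, but the tables do not drive escalation.
- A reader might infer that the data for a split are already on file. Pre- and postdose recording is required, but no section specifies an AE start time or a pre/postdose field, and the attributes listed in 11.3 include neither.

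**Conclusion.** The concern holds for two cases: AEs that start on Day 1 before the injection, and events that start on Day -7 before the first tablet. For the first, the stated rule attributes an event to a treatment not yet given, and it conflicts with protocol 9.3, the pre/postdose recording and SAP 18.3. For the second, Appendix 2 conflicts with protocol 10.2.1 and with SAP 18.1's own opening text.

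The size is modest. Randomised drug cannot influence a predose onset, and the rule is the same for active and placebo. The result is therefore misattribution and noise, with incidence overstated in the injection columns, and no expected bias in the contrast. A row for one dose group can move by up to 16.7 points per affected subject, subject to the condition in step 2. The frequencies in step 3 rest wholly on assumed rates and, in the first table, an assumed injection time. Injection-site reactions caused by the injection are not affected, since they cannot precede it.

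**What to change.** **SAP 18.1, 7.2 (AE clause) and Appendix 2.** Classify AEs that start on Day 1 or Day -7 by a pre/postdose flag or by start time relative to dosing. A predose Day 1 onset goes to the oral period unless it later worsens, which the existing worsening rule in 18.1 then handles. A predose Day -7 onset is a pretreatment event. Where timing is unknown, keep the date rule and flag the case in the AE listing.

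**AE case report form.** Add the flag or a start time for AEs that begin on a dosing day.

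**Protocol.** Align 10.5.3.1 and Table 2 with 10.2.1, so that events before the Day -7 tablet are recorded as pretreatment events. Reconcile 11.3 and 14.3.5.1 with the same definition.

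The cost is SAP and protocol wording plus one data item for AEs that begin on a dosing day. The SAP change should be settled before unblinding.
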